12.2 Data Analysis

All analyses will be performed using analysis files created by adding follow-up data to the main DISC database with verification by manual checking. SAS (SAS Inst., Cary, NC) will be the primary software used for analysis supplemented with S-Plus (Insightful Corp., Seattle, WA) and Stata (Stata Corp., College Station, TX).

Because DISC was a clinical trial, analysis of the specific aims will be performed by randomized treatment assignment. Mean serum progesterone will be compared between the intervention and usual care groups without regard to compliance with the intervention, attendance at intervention sessions, or attendance at earlier DISC clinic visits. Because hormonal contraceptives contain progesterone, only women not using hormonal contraceptives will be included in analysis of treatment group differences in serum progesterone levels. The distribution of serum progesterone values will be examined to determine whether transformation is appropriate prior to analysis. In previous DISC analyses, we In transformed hormone concentrations to improve normality and decrease dependence of the variance on concentration. We anticipate that In transformation of progesterone data collected at the proposed follow-up visit will also be appropriate, but a final decision will be made after examining the data. The analytical approach will depend on the distributions of age, race, and menstrual cycle day when blood was collected at the clinic visit in the two treatment groups. These characteristics are potential confounders that would not be affected by the intervention. If the treatment groups are balanced on these characteristics, means can be estimated directly and statistical significance of the treatment group differences can be tested using a Student's t-test. If the participants in the treatment groups are not balanced on these characteristics and there is evidence for confounding, we will estimate adjusted means and test for statistical significance using linear models. We used analysis of covariance to compare adjusted treatment group means in previous DISC hormone analyses.

The effect of missing progesterone data on observed treatment group differences will be evaluated using the multiple imputation method of Rubin [89], in which multiple datasets are constructed, analyzed, and results combined so that the underlying variability of the outcome is preserved.

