12.3.1 Primary Specific Aim

We used data from the DISC last visit on serum progesterone levels in 9 usual care group participants whose blood was collected 1-6 days before the start of their next menses. This time frame is the window during which follow-up visits will take place in the proposed study. Earlier DISC analyses were performed on In transformed hormone values. We also used In transformed values to improve normality of distribution for these power calculations. The mean transformed progesterone concentration adjusted for age and cycle day was 6.76 (sd = 0.52). Hormones will be measured only in participants not using hormonal contraceptives. CDC estimates that 40% of women 20-24 years old use hormonal contraceptives [146]. In our pilot study of DISC participants, 48% of women reported using hormonal contraceptives and 10% were pregnant. Ninety-three percent of participants in our pilot said they would be willing to come to a follow-up visit. We estimated detectable differences in progesterone concentrations at 80% (conservative) and 90% participation rates assuming 50-60% of participants are using hormonal contraceptives or pregnant and cannot be included in these analyses (Table 1). Depending on participation rate, hormone use, and pregnancy we will be able to detect

Table 1. Minimal Detectable Differences For Luteal Phase Progesterone and Estradiol at α =.05 (2-sided) and 80% Power

| Participation Rates | Hormonal Contraceptive Use or Pregnant | Number per Group | Detectable Difference Progesterone | | Detectable Difference Estradiol | |
|------------------------|--|---------------------|---------------------------------------|---|------------------------------------|---|
| | | | In | % | In | % |

| 80% | 50% | 60 | .266 | 23.3% | .164 | 15.1% |
|-----|-----|----|------|-------|------|-------|
| | 60% | 48 | .297 | 25.7% | .183 | 16.7% |
| 90% | 50% | 68 | .250 | 22.1% | .154 | 14.3% |
| | 60% | 54 | .280 | 24.4% | .173 | 15.9% |

22%-26% lower progesterone levels in the intervention group compared to usual care ((e $^{6.76}$ – e $^{6.76}$ - $^{2.266}$)/e $^{6.76}$). At last DISC visits the intervention group's mean progesterone level was 52.9% lower than the usual care group. We will have ample power to detect a difference that is less than half as large as this.

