12.3.2 Secondary Specific Aims

Luteal Phase Serum Estradiol: We used data from the DISC last visit on serum estradiol levels in 9 usual care group participants whose blood was collected 1-6 days before the start of their next menses. The mean In transformed estradiol concentration adjusted for age and cycle day was 2.62 (sd=.32). We estimated detectable differences in estradiol concentrations at 80% and 90% participation rates and assuming 50% -60% of participants are using hormonal contraceptives or pregnant and cannot be included in these analyses (Table 1). We will have 80% power to detect 14%-17% lower estradiol levels in the intervention compared to the usual care group.

Bone Mineral Density: We used data from Teegarden [147] to estimate the detectable differences in total body bone mineral density. Teergarden used DEXA to measure total body bone mineral density in 215 women 18-31 years old (mean age = 23.8 years). Their mean total body bone mineral density ranged from 1.00-1.37 gm/ cm² with a mean of 1.16 gm/cm² (sd = .08). This standard deviation is comparable to the population standard deviation of .087 in the Hologic Reference Data. With 80%-90% participation rate and 10% excluded because of pregnancy, we will have DEXA data on 108 – 122 women per group. This yields 80% power to detect treatment group differences in total body bone mineral density of .029 - .030 gm/cm².

Breast Density: We used data from Lee [95] to estimate detectable differences in percent dense (fibroglandular) breast tissue in intervention vs. usual care group DISC participants. Lee measured fatty and fibroglandular tissue volumes by MRI in the breasts of 40 women 20-83 years old. Because breast density changes with age and menopausal status and all DISC participants at follow-up visits will be 25-29 years old and premenopausal, we only used data from 15 women 20-45 years of age. Their percent dense tissue ranged from 18% - 83% with a mean of 45.1% (sd = 17.7%). With 80%-90% participation rate and 10% excluded because of pregnancy, we will have MRI data on 108 - 122 women per group. This yields 80% power to detect treatment group differences in percent dense breast tissue of 6.3% - 6.7%.

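### The primary test may be an unadjusted t-test, but Table 1's 80% power rests on SDs reported with age- and cycle-day-adjusted means, so that power is supported only for an adjusted analysis

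*Protocol*

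**What the plan says.** Protocol section 12.2 lets the data decide the primary analysis: "The analytical approach will depend on the distributions of age, race, and menstrual cycle day when blood was collected". There are two branches.

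- Balanced: "If the treatment groups are balanced on these characteristics, means can be estimated directly"; the test named is Student's t-test.
- Imbalanced: "If the participants in the treatment groups are not balanced on these characteristics and there is evidence for confounding, we will estimate adjusted means"; the test then comes from linear models.

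Neither balance nor evidence of confounding is given a criterion, and no analysis is named for imbalance without such evidence. The same section says that previous DISC hormone analyses used analysis of covariance, and that the secondary aims follow the primary approach (breast MRI apart).

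The power calculation is in section 12.3. Its progesterone input comes from "serum progesterone levels in 9 usual care group participants whose blood was collected 1-6 days before the start of their next menses", and section 12.3.1 reports: "The mean transformed progesterone concentration adjusted for age and cycle day was 6.76 (sd = 0.52"). Section 12.3.2 treats estradiol in the same way: "The mean In transformed estradiol concentration adjusted for age and cycle day was 2.62 (sd=.32"). No unadjusted SD is given for either hormone. From these inputs Table 1 states detectable differences at two-sided 5% and 80% power.

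**The concern.** The test and its power basis are both fixed in this Protocol, and they do not match. Balance on cycle day means that it does not bias the comparison. It does not stop progesterone from varying with cycle day inside each arm, and the t-test leaves that variation in its error term. A linear model with cycle day takes it out.

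Randomization makes approximate balance the likely case, although the analysed women are a subset (those not using hormonal contraceptives and not pregnant). The branch that Table 1 does not describe is thus the one most likely to be used. The Protocol itself regards cycle timing as important: section 7.5 has staff telephone weekly until the date of next menses is known, because it is needed to interpret the hormone data. The default test then leaves it out.

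At stake are some power for the primary aim and for estradiol, and a primary estimate whose form depends on a judgement made after the data are seen, with no stated threshold.

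**Working it through.** **Inputs.** From the Protocol: SD 0.52 (12.3.1) and 0.32 (12.3.2), two-sided alpha 0.05, 80% power, and 60, 48, 68 or 54 women per group (Table 1). Not in the Protocol: the share of variance R² that age and cycle day explain. It is assumed here over 0 to 0.50.

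**1. Reproduce Table 1.** Detectable difference = SD × (1.960 + 0.8416) × √(2/n).

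| n per group | Progesterone, computed (stated) | Estradiol, computed (stated) |
|---|---|---|
| 60 | .2660 (.266) | .1637 (.164) |
| 48 | .2974 (.297) | .1830 (.183) |
| 68 | .2498 (.250) | .1537 (.154) |
| 54 | .2804 (.280) | .1725 (.173) |

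The group sizes also reproduce: 301 × 0.80 × 0.50 / 2 = 60.2, and likewise 48.2, 67.7 and 54.2. So 80% power holds for a test whose error SD is 0.52 (or 0.32).

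**2. Error SD of the t-test.** If 0.52 is the residual SD, the unadjusted SD is 0.52 / √(1 − R²).

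**3. Power of the t-test at n = 60 and a ln difference of .266.** Power = Φ(.266 / (SD × √(2/60)) − 1.960). For R² = 0.20: SD = 0.52 / √0.80 = 0.581; standard error = 0.581 × 0.1826 = 0.106; .266 / 0.106 = 2.506; Φ(0.546) = 70.7%.

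| Assumed R² | Unadjusted SD | t-test power | Detectable at 80% power, n = 60 |
|---|---|---|---|
| 0 | 0.520 | 80.0% | .266 (23.4%) |
| 0.05 | 0.534 | 78.0% | .273 (23.9%) |
| 0.10 | 0.548 | 75.7% | .280 (24.4%) |
| 0.20 | 0.581 | 70.7% | .297 (25.7%) |
| 0.30 | 0.622 | 65.0% | .318 (27.2%) |
| 0.50 | 0.735 | 50.8% | .376 (31.4%) |

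The other rows of Table 1 lose the same power to within about 0.2 points. Put differently, R² = 0.20 reduces 60 women per group to the equivalent of 60 × 0.80 = 48, which is why .297 is also Table 1's entry for 48.

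**4. Estradiol.** The same factor applies. At R² = 0.20 and n = 60 the detectable difference is .1637 / √0.80 = .183, a 16.7% reduction instead of 15.1%.

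**5. The difference seen at the last DISC visit.** A 52.9% reduction is −ln(1 − 0.529) = 0.753. At R² = 0.50 and n = 48: 0.753 / (0.735 × √(2/48)) = 5.02; Φ(5.02 − 1.96) = 99.9%.

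**6. Precision of the SD.** The 95% interval is 0.52 × √(df/χ²): about 0.35 to 1.00 with 8 degrees of freedom, or 0.34 to 1.15 with 6 (two covariates fitted).

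**The case against.** **The size is unknown.** A reader might infer that the stated power is not delivered. The Protocol does not support that: it gives neither an unadjusted SD nor an R². Up to an R² of about 0.05 the loss is within 2 points. The losses of 10 to 30 points need an R² of roughly 0.20 to 0.50, for which it offers no source. Section 5.2 aims visits at 3-4 days before expected menses with a ±2 day window, which limits the spread of cycle days, although the date is only an expected one. This objection stands.

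**The SD may not be a residual SD, and it is imprecise.** The text attaches the adjustment to the mean and gives the SD in brackets. A residual SD is the natural reading but is not stated. With 9 women and two covariates, a residual SD need not be below the raw one, and the interval in step 6 can outweigh the adjustment effect. This also stands, but it weakens Table 1 for either test and does not reconcile the two sections.

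**Type I error.** A reader might infer that a data-dependent rule inflates false positives. The Protocol sets no threshold, so its own rule cannot be evaluated. Simulation with an assumed balance criterion gave about 4-5%, which is at or slightly below nominal. An unadjusted comparison of randomized groups is a valid test; what is lost is efficiency and prespecification.

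**Transformation.** Section 12.2 anticipates the ln scale, "but a final decision will be made after examining the data". Final confirmation is commonly left to an analysis plan, so this is minor.

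**Adjustment has its own risk.** Cycle day is observed after randomization, and section 2.1.3 hypothesizes lasting effects on the hypothalamic-pituitary-ovarian axis, so adjusting might absorb some effect. But section 12.2 itself holds that age, race and cycle day would not be affected by the intervention, and it already allows adjustment for them.

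**Conclusion.** The mismatch is real. Table 1 reproduces from SDs reported with adjusted means, while the only test named for balanced arms is unadjusted. The claims of 80% power for 22%-26% lower progesterone and 14%-17% lower estradiol are supported for an analysis adjusted for age and cycle day, and are unsupported, probably optimistic, for the t-test.

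The amount cannot be fixed from the Protocol. It runs from about 2 points of power at an assumed R² of 0.05 to about 29 points at 0.50, taking 0.52 as the residual SD. The study's ability to detect a difference as large as the 52.9% seen at the last DISC visit is not threatened by this mismatch, given that SD. This is a matter of consistency, efficiency and prespecification, not of an invalid test. It is worth correcting mainly because the remedy is nearly free.

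**What to change.** In section 12.2, replace the balance-dependent rule with one prespecified primary analysis: a linear model (ANCOVA) on ln progesterone with treatment, age, race and cycle day, fitted whatever the observed balance. Use the same model for ln estradiol. Define cycle day once, preferably on the scale used to select the planning data (days before the start of next menses), and state how women whose next-menses date is missing will be handled. In section 12.3, say explicitly that 0.52 and 0.32 are residual SDs, if they are.

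The cost is wording, a few degrees of freedom and the rule for missing menses dates. The covariates are already collected, and the approach matches previous DISC hormone analyses.

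If the t-test is kept instead, state the unadjusted SDs from the same 9 women and recompute Table 1 and the detectable differences quoted from it.

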7.2 Anthropometry

Height will be measured by a stadiometer and weight will be measured by an electronic scale. Participants will be clothed in a hospital gown without shoes. Consistent with earlier DISC measurement acceptability criteria, if height measurements do not agree within .5 cm or if weight measurements do not agree within .2 kg, measurements will be performed a third time and the two closest values will be averaged.

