7.11.4 Image Analysis

Image data will be processed at UCSF using customized image processing software. Bone mineral content (BMC) and bone area (AREA) will be measured and bone mineral density (BMD) will be calculated. BMC is the bone mass in grams of the region being measured and AREA, in square centimeters, is the area projected by the bone in a 2-dimensional x-ray image. BMD is the value most reported as DEXA bone density. It is found by dividing the BMC/AREA and is in units of grams per square centimeters, or g/cm². Bone density as measured by DEXA techniques is an areal density, not a true physical density (mass per unit volume). This is because the DEXA measure is derived from 2-

dimensional x-ray projections. Thus, DEXA bone density is affected by bone size as well as physical density, and areal BMD will always be confounded by bone size (e.g. participant height) unless corrected. There are several techniques to accomplish this. Carter [141] derived "bone mineral apparent density" or BMAD that takes into account that the spine vertebral body is close to cylindrical in shape and this information can be used to estimate the missing dimension. It was shown that BMAD = BMC/(Bone projected area)^{1.5}. The UCSF investigators have also derived a whole body apparent density that effectively removes bone size from whole body BMD[142]. We will derive these apparent density variables in our analysis to reduce the data scatter caused by participant differences. Any abnormalities will be reported to the participant's physician.

In addition to bone density, the whole body scan provides body composition. DEXA is the most precise method to estimate whole body percent fat, and the CV for repeated scans is ~1% [143]. This is part of the whole body protocol and requires no additional radiation or time. Because breast density and bone density are strongly correlated to body composition, the %fat will be used in multivariate analyses of these two outcome variables.

It is not anticipated that abnormalities will be detected by DEXA. However, if abnormality is detected, the participant will be informed and the results will be sent in writing by the clinical center PI to the physician identified by the participant on the consent form.

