In secondary analysis of the primary aim, we will determine whether treatment group differences in progesterone are related to differences in several individual characteristics including age at menarche, BMI, and % body fat by including appropriate covariates in linear models. We will investigate if there is a particular component of the diet intervention (energy, total or saturated fat, fiber) responsible for observed differences in progesterone levels. BMI and diet at time of the follow-up visit or earlier, during puberty, could be responsible for observed treatment group differences in progesterone at the follow-up visits. To evaluate if puberty is a critical time for exposure, we will estimate the mean level of exposure at earlier DISC visits and use linear models to evaluate whether

average pubertal exposure can explain treatment group differences in progesterone levels at the follow-up visit. Furthermore, we will evaluate potential confounding and effect modification of treatment group differences in progesterone levels at follow-up visits by changes in characteristics such as diet, anthropometry, and physical activity between the last DISC visit and the follow-up visit and by intervening events such as pregnancy, lactation, and use of hormonal contraceptives, by including terms for main effects in models to evaluate confounding and by including cross-product terms in models that include main effects to evaluate effect modification.

Analysis of secondary aims will be performed using the same approach as described for the primary specific aim except breast MRI analysis will use statistical techniques for paired organs as described below. Similar to progesterone, women using hormonal contraceptives will not be included in analysis of serum estradiol. We will, however, perform breast MRI and bone densitometry on these women. In analysis of treatment group differences in breast density and bone density, we will evaluate confounding by past and present hormonal contraceptive use. We also will test for interaction of hormonal contraceptive use with treatment group effects by including cross-products terms in models. Analyses will be stratified by hormonal contraceptive use if cross-product terms are significant.

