12.3 Sample Size and Power

Participants in the proposed study are the 301 female DISC participants. Because this is an existing cohort and sample size is set, we estimated detectable differences in luteal phase progesterone levels (our primary specific aim). For information, we also provide detectable differences for our secondary specific aims. Detectable differences in treatment group means were calculated using S-Plus 2000 (Insightful, Seattle WA).

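### The planned comparisons of bone density and breast density never use height and BMI from before randomization, which could add precision without bias; the protocol does not let the gain be fixed

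*Protocol*

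**What the plan says.** Section 12.2 sets the rule for progesterone first: "The analytical approach will depend on the distributions of age, race, and menstrual cycle day when blood was collected". If the groups are balanced on those three characteristics, means are compared directly with a t-test. If they are not, and confounding is evident, adjusted means come from a linear model. The three are justified as characteristics that the intervention could not affect.

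The section then extends the rule: "Analysis of secondary aims will be performed using the same approach as described for the primary specific aim". For breast density the test is replaced by GEE, to allow for two breasts per woman. For both density outcomes it adds a check of confounding by, and interaction with, hormonal contraceptive use.

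Section 7.11.4 treats body size separately. It says that areal bone density is confounded by bone size unless corrected, and it plans apparent-density variables as the correction. It also says "Because breast density and bone density are strongly correlated to body composition", and on that ground plans to use percent fat from the follow-up scan in multivariate analyses of both outcomes.

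On data from the original trial, section 12.2 says "All analyses will be performed using analysis files created by adding follow-up data to the main DISC database". Section 7.2 refers to height and weight as measured earlier: "Consistent with earlier DISC measurement acceptability criteria, if height measurements do not agree within .5 cm". Section 2.0 gives the age at randomization as 8 to 10 years.

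**The concern.** The protocol names body size and composition as strong correlates of both density outcomes, yet its rule for comparing the groups on those outcomes turns on three other characteristics. Adjustment is triggered by observed imbalance, so reducing residual variance is not one of its purposes.

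This matters because the sample cannot grow: "Participants in the proposed study are the 301 female DISC participants". Precision has to come from measurement or from analysis. Height and BMI at 8 to 10 years precede the intervention, so adjusting for them cannot remove any of its effect. If they predict adult bone or breast density, leaving them out gives up power on the two aims that use the most women, 108 to 122 per group.

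**Working it through.** **Does any planned analysis already do this?**

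- *Main comparison (section 12.2):* age, race and cycle day, conditional on imbalance, plus a check of contraceptive use. No body-size term.
- *Percent fat (section 7.11.4):* enters models for both outcomes, but is measured at follow-up. Section 12.2 itself examines BMI and percent body fat as possible explanations of a group difference in progesterone. Adjusting for percent fat may therefore take out part of the effect under study. Follow-up height would have a similar weakness, since section 2.1.2 regards adult height as shaped by diet in childhood.
- *Apparent bone density (section 7.11.4):* addresses bone size only, and only for aim 3.
- *Secondary models (section 12.2):* use BMI and average pubertal exposure, to explain a group difference rather than to estimate it.

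None of these is a covariate fixed before randomization and used for precision in the randomized comparison.

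**Inputs (sections 12.3.1 and 12.3.2).** Two-sided alpha 0.05 and 80% power (stated for the hormone table, taken to apply here). SD 0.08 g/cm² for total body bone density and 17.7 percentage points for percent dense tissue. Participation 80% to 90%, with 10% excluded for pregnancy.

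**Reproducing the stated figures.**

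Women per group, with about equal allocation: 301 × 0.80 × 0.90 / 2 = 108.4 and 301 × 0.90 × 0.90 / 2 = 121.9, matching 108 and 122.

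Detectable difference = SD × √(2/n) × (1.960 + 0.842):

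- Bone density: 0.08 × √(2/108) × 2.802 = 0.0305, and 0.0287 at n = 122. Stated: 0.030 and 0.029.
- Percent density: 17.7 × √(2/108) × 2.802 = 6.75, and 6.35 at n = 122. The protocol says "This yields 80% power to detect treatment group differences in percent dense breast tissue of 6.3% - 6.7" (percentage points).

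The figures reproduce from unadjusted SDs, with no covariate gain assumed.

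**Effect of a baseline covariate.** Let rho be the correlation of baseline height and BMI, taken together, with the outcome. The residual SD is SD × √(1 − rho²). The documents give no value of rho, so a range is shown. Power is at the stated differences (0.030 and 0.029 g/cm²; 6.7 and 6.3 points), by normal approximation. Each cell gives n = 108 / n = 122.

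| rho | √(1 − rho²) | Detectable, bone | Detectable, breast | Power, bone | Power, breast |
|---|---|---|---|---|---|
| 0 | 1 | 0.0305 / 0.0287 | 6.75 / 6.35 | 78.7% / 80.8% | 79.4% / 79.4% |
| 0.2 | 0.980 | 0.0299 / 0.0281 | 6.61 / 6.22 | 80.3% / 82.4% | 81.0% / 81.0% |
| 0.3 | 0.954 | 0.0291 / 0.0274 | 6.44 / 6.06 | 82.3% / 84.3% | 83.0% / 83.0% |
| 0.4 | 0.917 | 0.0280 / 0.0263 | 6.18 / 5.82 | 85.2% / 87.1% | 85.9% / 85.8% |
| 0.5 | 0.866 | 0.0264 / 0.0249 | 5.84 / 5.50 | 88.9% / 90.5% | 89.5% / 89.4% |

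The gain in power is 1.6 points at rho 0.2, about 3.5 at 0.3, about 6.5 at 0.4 and about 10 at 0.5. A noncentral-t calculation that charges two degrees of freedom gives nearly the same: for breast density, 79.1% rising to 82.7%, 85.6% and 89.2% at rho 0.3, 0.4 and 0.5. Like the protocol's own calculation, this uses one SD per woman and does not model the two breasts separately.

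**The case against.** The strongest objection is that the protocol does deal with body size for exactly these outcomes. A reader of section 12.2 alone might infer that body-size variance is left wholly in the error term, or that a hormone covariate list was simply reused. Neither is supported. Section 7.11.4 plans percent fat for both outcomes and a bone-size correction for aim 3, and section 12.2 adds contraceptive use specifically for them. Where those measures are applied, a baseline covariate would probably add less than the table shows; that smaller gain was not calculated. What does not follow is that these measures replace baseline adjustment, for the reasons given in the working.

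Second, the size of the gain has no support in the documents. The correlation stated in section 7.11.4 is with body composition as an adult, not at 8 to 10 years. At rho 0.2 the detectable difference shrinks by only 2%. This stands in full.

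Third, no sentence says that randomization-visit height and weight are held. Sections 7.2 and 12.2 make it very likely, but it remains an inference.

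Fourth, precision covariates for secondary outcomes are often left to an analysis plan, and none is available here. That would answer a complaint about silence. But section 12.2 is not silent: it states a rule for when covariates enter, and a later plan would have to depart from it.

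**Conclusion.** The point holds as a low-cost efficiency improvement for aims 3 and 4. The randomized comparison in section 12.2 is unadjusted by default, admits covariates only on observed imbalance, and never uses body size from before randomization. The body-size measures in section 7.11.4 do not supply an unbiased precision gain for both outcomes.

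A reader might go further and infer that the detectable differences in section 12.3.2 are wrong, or that the unadjusted comparison is biased. The documents support neither: the figures reproduce, and a comparison by randomized group is valid without adjustment.

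The gain runs from under 2 power points at rho 0.2 to about 10 at rho 0.5, where the detectable difference in percent density falls from the stated 6.3 to 6.7 points to about 5.5 to 5.8. It could be smaller for apparent bone density, which already removes bone size. The conclusion rests on an assumed rho and on the randomization-visit values being in the DISC database.

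**What to change.** In section 12.2, replace the carried-over rule for aims 3 and 4 with one pre-specified main model per outcome: linear for bone mineral density and GEE for breast density. Each contains treatment, height and BMI from the DISC randomization visit, and the demographic terms already named (age and race), regardless of observed balance. First confirm that the randomization-visit values are held. Label the models with follow-up percent fat as secondary or explanatory, so that sections 7.11.4 and 12.2 agree on which result is the main one. The progesterone and estradiol analyses need no change on this account.

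The cost is wording, about two degrees of freedom per model, and simple imputation of any missing baseline value. No new data collection is needed. Fixing the covariates in advance also removes the data-dependent choice between adjusted and unadjusted results for these two aims.
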